**Table 4. Study Assessment Schedule**

Measures	EMA	Baseline	Pre-Treatment	Weekly Phone	During Treatment	Post-Treatment	3-Month	6-Month
Demographic Information		X						
Pain and Treatment History		X						
Start Back Tool		X						
Pain Medication Questionnaire (PMQ)		X						
Roland Morris Disability Questionnaire SF (RMDQ)		X						
PROMIS Pain Interference	X		X			X	X	X
Pain Appraisal Scale (PAS)	X		X	X		X	X	X
2-item Catastrophizing Scale from the Coping Strategy Questionnaire (CSQ)			X	X		X	X	X
Pain-Related Cognitive Process Questionnaire (PCPQ) Non-Judgment Scale	X		X	X		X	X	X
Godin Leisure-Time Exercise Questionnaire	X		X			X	X	X
Hours Spent Sitting w/o Exercising	X							
Pain Intensity NRS	X	X	X	X		X	X	X
Positive and Negative Affect Schedule (PANAS)	X		X			X	X	X
PROMIS-29 Sleep Disturbance			X			X	X	X
PROMIS-29 Physical Function			X			X	X	X
PROMIS-29 Depression			X	X		X	X	X
PROMIS-29 Anxiety			X	X		X	X	X
PTSD Checklist (PCL-C)			X			X	X	X
Medication & Cannabis Use			X	X		X	X	X
UW Pain-Related Self-Efficacy Scale	X		X			X	X	X
Participant Engagement					X a			
Working Alliance Inventory (WAI)	X b							
Group Climate Questionnaire (GCQ-S)	X b							
Duration and Times Practicing Skills	X					X	X	X
Sleep/Wake Times	X							
Health Care Utilization			X			X	X	X
Pleasant Events Schedule SF			X			X	X	X
Behavioral Activation for Depression Scale (BADS)			X			X	X	X
Global Quality of Life			X			X	X	X
Employment Status	X	X				X	X	X
Weight	X	X				X	X	X
Mindful Awareness and Attention Scale (MAAS)			X			X	X	X
Pain Resilience Scale			X			X	X	X
Pain-Related Cognitive Process Questionnaire (PCPQ) – Full			X			X	X	X
Control, Harm, Disability, and Medication Scales from the Survey of Pain Attitudes (SOPA)			X			X	X	X
PROMIS Cognitive Function Abilities			X			X	X	X
COVID-19 Impact Questions			X			X	X	X
Treatment Credibility and Expectancies	X c							
Patient Global Impression of Change (PGIC)						X	X	X
Patient Global Assessment of Treatment Satisfaction (PGATS)						X	X	X
Treatment Modality & Preferences						X		
Importance of Treatment Outcomes	X						X	
Qualitative Outcomes							X	
Optional Measures: Positive & Negative Response to Pain Scales, Future Self Questionnaire (FSQ), Valued Living Scale (VLS)			X			X	X	X

aWill be assessed for each participant and reported by the clinician following every treatment session. bWill be assessed during the evening EMA following Sessions 4 & 8 only. cWill be assessed once before Session 1 and once following Session 1 but before Session 2.

## **D6g. Treatment Fidelity Monitoring**

We will take a number of steps to ensure uniform treatment protocol delivery. First, all treatments will be provided by a Masters-level or postdoctoral senior fellow or licensed psychologist (the study “clinician”) who has at least two years of clinical experience in delivering psychosocial treatments or by one of the study investigators. The clinician will be trained and supervised by the investigators who have a great deal of experience in providing the study treatments. If one of the study clinicians is unable to deliver a session as planned, and no other study clinicians are available to fill in, a clinician who has experience in delivering the treatment content may be asked to fill in during emergency situations. This emergency clinician would have documentation of training from any of the study investigators or consultants demonstrating training in the content of the session being covered. Second, the clinician will be provided with a detailed treatment manual and protocol outline. Third, Drs. [name] (CT intervention), [name] (MM intervention), or [name] (AS intervention) will provide regularly scheduled supervision to the study clinicians. Weekly supervision will occur for the first two cohorts of every study clinician new to the program; these are anticipated to become less frequent as the clinicians gain more experience and the need for frequent supervision sessions decreases. However, all clinicians at all times will have easy access to the clinical supervisors (either in person, via telephone, via email, or via Skype) at any time between the supervisory sessions as needed and as issues arise. Fourth, adherence and fidelity will be monitored using session audio recordings. Masters-level or above clinicians supervised by the investigators will review a random selection of 25% of the recordings (2-3 randomly selected sessions per group, to be coded by the start of treatment for the following cohort) to ensure procedures are followed. Protocol quality and adherence criteria will be developed for each session with satisfactory adherence defined as  $\geq 90\%$  of the maximum possible score. Corrective feedback will be provided to the clinician during regularly scheduled supervision sessions; didactics and role plays to correct “drift” will be implemented if needed.

## **D6r. Data Collection and Management**

### **Overview**

Data will be collected at the University of Washington via telephone, online, or in person in an outpatient setting with the following two exceptions:

1. Ecological Momentary Assessment (EMA) data, which will be entered by the participant via a web portal (desktop, laptop, tablet, mobile device);
2. ActiGraph data, which will be collected via the ActiGraph device the participant will wear during participation in the study.

All study data collected for purposes of data analysis will be de-identified, labeled with a code number that is unique to each research participant, and maintained separate from any identifying information. The participant code numbers will consist of an arbitrary number consecutively numbered in order of screening/medical record review/approach. An electronic Master List key code will be maintained that links the participants with their code number. This key code along with identifying information will be stored in a password-protected Microsoft Access database that does not contain any study data. This database will also reside in a limited access folder on the UW network drive. Only approved study personnel will have access to the Master List key code, participant identifying information, and de-identified study data. We will analyze and report participant data in aggregate form and no PHI will be entered into these analyses or reports.

De-identified data collected by research staff or online will be entered directly into a database created in REDCap, a secure HIPAA-compliant web-based system. Web forms will be created to enhance functionality and proper data entry. The REDCap system also allows researchers to create an audit trail, as well as capture an e-signature from research staff attesting to the validity of the data entered. Both pieces will be utilized during data collection (i.e., we will create audit trails and require research staff to provide electronic signatures on all our electronic case report forms). Data will be downloaded to a limited access folder on the secure UW network drive.

Ecological Momentary Assessment (EMA) data will also be encrypted and stored on a HIPAA- and IRB-compliant web-based storage database. The EMA data will also be downloaded and stored in a limited access folder on the secure UW network drive.

Lastly, ActiGraph data is temporarily stored on the actual ActiGraph device until the participant returns the device to researchers. The data will then be downloaded by research staff and stored in a limited access folder on the secure UW network drive.

### **Recruitment and Screening**

Trained study personnel will conduct the screening interview either in person or via telephone at the UW using a structured format in which the interviewer asks questions from a script. Study personnel will note the answers directly into a database if conducted via telephone or on the case report form if conducted in person. An electronic screening form as part of a REDCap database will be used to guide the screening to ensure that the same information is gathered and coded for all participants. Also, study personnel will enter basic recruitment outcome data for each prospective participant approached directly into the database using a standardized electronic case report form.

### **Telephone and Online Assessments**

The self-report extended assessments consist of standardized protocols with specific/scripted questions. All study personnel who will be gathering data from these sources will be trained by the PIs regarding the collection of data and will have professional education and training as required by these instruments. Study personnel will enter the telephone assessment data directly into the database using a standardized electronic form in REDCap.

If the participant completes the self-report assessments online, they will be provided a secure link to a standardized electronic form in REDCap. The participant will directly complete the survey in REDCap.

### **EMA Data**

Study participants will enter EMA data before, during, and after treatment. Study participants will be prompted via notifications to enter the data twice a day during those assessment periods. The data will be entered through a secure web portal with a link that is sent through (1) a notification on a smart phone; or (2) email, which can be accessed via desktop, laptop, tablet, or other mobile device. The data will then reside in a HIPAA- and IRB-compliant cloud-based storage database. Study personnel will check the EMA data in this database periodically to ensure participant compliance. In addition, study personnel will regularly download the data for storage in a limited access folder on the secure UW network drive.

### **ActiGraph Data**

Activity levels will be measured before, during, and after treatment using the ActiGraph wGT3X-BT, which uses triaxial accelerometry. The participant will be instructed to wear the ActiGraph device on their non-dominant wrist during those periods of time. Each ActiGraph monitor will be initialized with the participant ID number for each specific participant prior to the device being sent to the participant. No identifying information is programmed into the device (although we will input the participant's study ID, planned wear location [i.e., wrist], side (right/left), height, weight, race, and sex, as reported to us by the participant). Thus, all activity and sleep data collected from participants will not contain any information that will reveal the identity of its user.

The participant will send back the ActiGraph to study personnel in a provided self-addressed stamped envelope at the end of the 4-Week Post-Treatment Monitoring Period. Study personnel will download the data collected by the ActiGraph and link it to the participant's other data via their participant identification number. The data will be stored in the same limited access folder on the secure UW network drive as the other data used for data analysis purposes. Data may be downloaded from the ActiGraph only with the assistance of ActiGraph software that is unavailable to the general population. That is, participants will NOT have the ability to download the data from the device itself (e.g., onto their personal computer).

### **Exceptions to Separation of Study Data from Identifying Information**

There are four exceptions to the protocol of separating all study data from participant identifying information.

1. The group treatment sessions will be audio recorded to make sure study clinicians are following study procedures. These recordings may also be used for training purposes. The study clinicians will notify participants before the start of the session that they will be recording the session. The recordings will be stored in a limited access folder on the secure UW network drive. Audio recordings will be (1) reviewed by study personnel and used for assessing fidelity to treatment study procedures by study clinicians, and (2) for training purposes. The audio recordings will not be labeled with any participant identifying information. The only identifying information that will be contained in the recordings will be participants' voices and if the study clinician or group members state a participant's name during the discussion.
2. The qualitative interviews collected after the conclusion of treatment will also be audio recorded. Specifically, unblinded research staff will use open-ended questions to interview participants about their experiences in the treatment program and collect study feedback, if any. Effective 2020, there will also be a question on COVID-19's impact during treatment. Research staff will notify participants before the start of the interview that they will be recording the interview. The recordings will be stored in a limited access folder on the secure UW network drive. Audio recordings will be transcribed (by third party software) and reviewed and coded by unblinded study personnel for themes that may highlight information about the program not captured by study outcome data. The audio recordings will not be labeled with any participant identifying information. The only identifying information that will be contained in the recordings will be the participant's voice and if the staff member states the participant's name during the interview. No blinded staff members will have access to these qualitative interviews.
3. Reminders/notifications to complete the EMA assessments will be sent to either a participant's email address or mobile phone number. The participant's unique ID number may be included in the reminder/notification, creating a crosswalk between the

participant's identity and participant data. Please note, however, that the EMA data that will be collected will not be stored with any identifying information.

4. Participants will be asked to complete a document outlining home practice completion. The document itself will not contain any identifying information, but since it will be on Google Drive, identifying information may be included (e.g., name or participant ID). The documents will then be downloaded from Google Drive and engagement in home practice data will be extracted and stored. The documents will be stored in a limited access folder on the secure UW network drive only accessible by unblinded research staff.

### **Hard Copy Data**

Any hard copies of study forms will be stored on a secure, badge-protected floor in the Ninth and Jefferson Building. Any hard copy forms containing participant identifiers will be stored in locked filing cabinets in a locked cabinet separate from the de-identified study data.

### Blinded/Unblinded Research Staff

The following table describes details regarding who among the study investigators and research staff will be blinded and when they will be blinded.

Staff Member	Blinded / Unblinded	When Blinded
[name].	Unblinded (Study Co-PI, will oversee data fidelity, provide supervision to study clinicians, participate in study analysis and reporting)	N/A
[name].	Unblinded (Study Co-PI, will provide supervision to study clinicians, participate in study analysis and reporting)	N/A
[name].	Blinded (will help manage outcome data, design and oversee randomization procedures, primary investigator responsible for data analysis)	Blind during data collection phase of study
[name].	Unblinded (will provide supervision to study clinicians, help address adverse events, participate in study analysis and reporting)	N/A
[name].	Unblinded (will administer intervention)	N/A
[name].	Unblinded (will administer intervention)	N/A
[name].	Unblinded (will administer intervention, may participate in study analysis and reporting)	N/A
[name].	Unblinded (will administer intervention)	N/A
[name].	Blinded (will not have access to study data or randomization assignment, may participate in study analysis and reporting)	Entire study
[name].	Blinded (will not have access to study data or randomization assignment, may participate in study analysis and reporting)	Entire study
[name].	Unblinded (will help manage unblinded data, may participate in study analysis and reporting)	N/A
[name].	Blinded (will not have access to study data or randomization assignment, may participate in study analysis and reporting)	Entire study
[name], B.S.	Blinded (will manage and collect outcome data); will not analyze or report data during data collection phase of study	Blind during data collection phase of study
[name], B.A.	Unblinded (will manage and collect unblinded data)	N/A

[name], B.S.	Unblinded (will help manage and collect unblinded data)	N/A
[name]	Blinded (will help manage and collect outcome data); will not analyze or report data during data collection phase of study	Blind during data collection phase of study
[name], B.S.	Blinded (will help manage and collect outcome data); will not analyze or report data during data collection phase of study	Blind during data collection phase of study
[name]	Unblinded (will only randomize participants to treatment)	N/A
[name]	Unblinded (will only randomize participants to treatment)	N/A

#### **D6s. Statistical Analyses**

The measures and assessment time-points administered in this sub-sample will match those that are collected as a part of the parent grant, with three exceptions. In addition, this sub sample will also complete the Pain Medication Questionnaire, PTSD Checklist-5 (PCL-5) and the PROMIS Anxiety scale; also, these three measures have been added to the parent study to allow for a replication test across samples (i.e. we will be able to perform the planned tests in a subset of patients with low back pain from the parent project who are taking opioids at baseline). Participants enrolled in the supplemental study will also additionally complete weekly assessments of their opioid use (as well as other mechanism variables) during the baseline, treatment, and immediate post-treatment phase. To facilitate recall for these, participants will be asked to have their medications physically available at assessments. Analgesic medication (both usual and rescue) data will be converted to standard equivalencies using the formulas developed at the UW Pain Relief Center (methadone for opioids, ibuprofen for NSAIDS, and phenobarbital for sedative-hypnotics).

*For Aim 1 of this supplemental study*, the primary moderator measures are: (1) the Coping Strategy Questionnaire, Pain Catastrophizing items; (2) the Pain-Related Cognitive Process Questionnaire, Non-Judging scale; and (3) ActiGraph assessed activity counts. Other moderators will also be examined in secondary analyses. The primary outcome will be baseline to post-treatment change in opioid use, as assessed in MMEs. The Aim 1 supplemental hypotheses will be tested via a series of three OGRS tests. Indicator coding will be used and these tests will be interpreted in the context of point estimates and confidence intervals. Effect sizes will be calculated for any moderation main effects or interactions emerging that have confidence intervals that do not contain zero, and these effects will also be probed using the Johnson-Neyman boundary of significance to determine at what level of the moderator is outcome influenced. The Johnson-Neyman procedure eliminates the need to probe at a variety of arbitrary points along the moderator and defines regions of significance and regions of non-significance. In our pilot work we have successfully implemented this statistical approach in a sample of N=69 individuals with low back pain to detect moderator main and interaction effects to provide a preliminary test of the LA&E model in a trial comparing MM, CT and Mindfulness-Based Cognitive Therapy (MBCT). This sample size provided sufficient power ( $\alpha \leq .05$ ) to identify: (1) an interaction effect for MM vs. MBCT ( $b = .09$ ,  $p < .05$ , Confidence Interval [CI]: .003 to .175), such that people with low baseline catastrophizing showed greater improvement

in pain intensity when assigned to MBCT ( $r = -.36$ ; within condition effect), with the boundary of significance identified as a Pain Catastrophizing Scale score of  $\leq 16.35$ ; (2) a further interaction effect for MM vs. MBCT ( $b = -.23$ ,  $p = .05$ , CI:  $-.46$  to  $.003$ ), showing that higher baseline mindfulness was associated with greater improvement in pain intensity in MBCT ( $r = .40$ ; within condition effect), with the boundary of significance identified as a Five Facet Mindfulness Questionnaire Observe Scale score of  $> 15.03$ . Thus, based on these effects in our pilot work testing the LA&E predictions, we anticipate that the proposed sample size for this supplemental project of  $N=90$  will be sufficient to detect medium to large effects (at the  $\alpha < .05$  level). Hypotheses 1a-1c would be supported if an interaction effect emerges (significant at the  $\alpha < .05$  level) and one or more of the within group effect sizes (of the moderator on the primary outcome) are medium or large.

*For Aim 2 of this supplemental study*, the primary mediator measures are: (1) a Numerical Rating Scale assessing characteristic pain intensity (in the past week); (2) the PROMIS Depression scale; and (3) the PROMIS Anxiety scale. Additional secondary mediators, selected per the primary mechanisms examined in the parent study (e.g., catastrophizing, mindfulness, activity level), will also be explored in the supplemental project sub-sample. The association between treatment-related changes in the primary mechanisms on changes in outcome will be tested via three PROCESS tests with 5,000 bias-corrected bootstrap resamples. The PROCESS bias-corrected bootstrap approach has been shown to consistently be the most powerful test of mediation (i.e., compared to the Sobel test, Baron and Kenny's approach) and is appropriate for small sample sizes. We will examine the significance of each path to determine if treatment condition has a differential effect on the mediator and/or outcome (although treatment-related differences in outcome are not expected), and whether early change in the mechanism is associated with later change in outcome. In the instance of a possible specific vs. shared mechanism effect, post-hoc associations will be tested via correlations to identify estimates of effect sizes for descriptive purposes.

We applied this approach to the three active treatments in pilot data obtained in our RCT comparing CT, Hypnosis and Hypnotic-CT (within the subsample of participants who reported musculoskeletal pain who were prescribed opioids,  $N=18$ ) to examine the relative statistical power achieved in that sample to detect medium to large effects for the analyses planned for this supplemental project. In two PROCESS models testing if early change in pain intensity or depression were specific vs. shared mechanisms in accounting for late treatment change in opioid use, results showed: (1) a non-significant effect of condition on outcome (path *c*) as well as on both mechanisms (path *a*); and (2) a significant effect of both mechanisms on the outcome (path *b*;  $ps < .01$ ). Post-hoc correlations were then conducted for descriptive purposes. We found that early change in both pain intensity and depression were significantly associated with later change in opioid use across groups ( $rs = .58$  and  $.68$ , respectively); on the other hand, early change in outcome was not significantly associated with later change in mechanism. Taken together, these results (1) provide support for early change in pain intensity and depression as underlying later reductions in opioid use, and (2) are consistent with a shared mechanisms account for the role of early change in pain intensity and depression as mechanisms driving decreased opioid use across the treatments studied in this pilot data. The proposed sample size and procedures of the supplemental project will afford the capacity to test these associations more definitively.

Overall, our pilot data indicate that if changes in outcome and mechanisms in the supplemental project are medium to large in nature, then the sample size of  $N=90$  will be adequate to test the mediation hypotheses 2a and 2b. Support for Hypothesis 2a and the shared mechanisms conceptualization would be found in the instance of a non-significant effect

of condition on the mechanism variable, but significant ( $\alpha \leq .05$ ) effect of the mechanism on outcome collapsed across groups. Support for Hypothesis 2b on the other hand would be found in the instance of a significant effect of condition on the mechanism, with change in the mechanism differentially associated with change in outcome across treatment conditions.

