#### A2a. Primary Aim and Hypotheses

**Aim 1: Test the LA&E model to investigate theory driven moderators of response to CT, MM, and AS.**

To accomplish Aim 1, we will use omnibus groups regions of significance (OGRS) tests to evaluate the effect sizes associated with the extent to which baseline pain catastrophizing, mindfulness, and activity level are respectively associated with reductions in opioid use following CT, MM, and AS.

**Hypothesis 1a:** Higher baseline levels of catastrophizing will be associated with greater reductions in opioid use in response to the CT intervention compared to MM or AS.

**Hypothesis 1b:** Lower baseline levels of activity will be associated with greater reductions in opioid use in response to AS compared to CT or MM.

**Hypothesis 1c:** Higher baseline levels of non-judgment will be associated with greater reductions in opioid use in response to MM compared to CT or AS.

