## D2. Study Timeline

We designed a four-year study plan and timeline for achieving short-term study objectives. There will be approximately 35 months available to enroll 90 participants. The anticipated lost to follow-up rate for this study is 20% of the total enrollment number, or 18 participants. We anticipate that with 90 participants enrolled (although we may elect to continue to enroll beyond this if we have the resources to do so, as this would provide even more power for the planned analyses) and a 20% attrition rate, we will have complete data for 72 of our participants; the primary analyses are to be conducted with the intent to treat sample.

Months 01-06 in Year 01 (Year 02 of the parent grant) will be spent finalizing internal operating procedures surrounding the study. Participant enrollment will require approximately 3 years (36 months; Month 07, Year 01 through Month 06, Year 04). Data collection and cleaning will be ongoing through Month 12, Year 04. Data analysis and dissemination will occur following data collection and cleaning. Drs. [name] and [name] will closely monitor study flow and will hold regular conference calls to coordinate study procedures. Both PIs will be directly involved with the details of the study at every level. Intra-site team meetings with staff and Co-Is will be conducted to ensure any issues will be addressed as they arise.

Milestone	Year 1*				Year 2*				Year 3*				Year 4*			
	1	2	3	4	1	2	3	4	1	2	3	4	1	2	3	4
Finalize administrative supplement protocol, data collection procedures, and obtain IRB approval	X	X														
Enroll 90 participants and execute study procedures			X	X	X	X	X	X	X	X	X	X	X	X	X	
Data analysis; evaluate benchmarks to determine whether to proceed to grant application for a larger study															X	X
Dissemination of study findings															X	X

\*Add one year for time corresponding to parent grant

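### The Aim 1 claim that N=90 is sufficient for medium to large moderation effects is not supported by the pilot it cites, and does not hold when the effect is confined to one arm

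*Protocol*

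**What the plan says.** Protocol D6s describes a pilot of 69 people with low back pain randomised to MM, CT or MBCT. It says of that pilot "This sample size provided sufficient power" and reports two MM vs. MBCT interactions on improvement in pain intensity:

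- with baseline catastrophizing: b=.09, p<.05, CI .003 to .175, r=-.36 within MBCT;
- with baseline mindfulness: b=-.23, p=.05, CI -.46 to .003, r=.40 within MBCT.

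From these it concludes that N=90 "will be sufficient to detect medium to large effects" at α<.05.

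On the test, D6s says the Aim 1 hypotheses "will be tested via a series of three OGRS tests", and then: "Indicator coding will be used and these tests will be interpreted in the context of point estimates and confidence intervals". Effect sizes are to be calculated for main effects or "interactions emerging that have confidence intervals that do not contain zero". Hypotheses 1a-1c "would be supported if an interaction effect emerges", significant at .05, and at least one within-group effect of the moderator is medium or large. Section A2a sets one arm against the other two; Hypothesis 1a, for example, concerns response "in response to the CT intervention compared to MM or AS".

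Section D5 expects 20% loss to follow-up, leaving 72 with complete data, and allows enrolment beyond 90. The SAP, dated July 23, 2024, contains neither a moderation analysis nor a sample-size justification.

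**The concern.** The sentence on N=90 reads as a power statement, but no power, effect metric or variance stands behind it. It is an inference from two pilot interactions that came out close to p=.05, and a result near .05 shows only that a result near .05 occurred.

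The pilot is also remote from Aim 1. This trial has no MBCT arm, and its outcome is change in MMEs. The pilot had no AS arm, and neither cited effect concerns activity level, so Hypothesis 1b has no cited pilot effect at all.

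What is at stake is how a null result is read. D6s says what would support Hypotheses 1a-1c but not how to interpret a non-significant interaction. The timeline in D2 plans to "evaluate benchmarks to determine whether to proceed to grant application for a larger study". A null interaction set against a statement of sufficient sample size would look like evidence against matching patients to treatments, when it might be uninformative.

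**Working it through.** **Inputs from the Protocol:** N=90 in three arms (about 30 each), 72 expected with complete data (24 each), α=.05, and the pilot estimates and CIs.

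**Assumptions of ours:** two-sided tests, equal arms, a normal moderator, equal outcome variance in each arm, r=.3 as medium and r=.5 as large, and 80% as a conventional yardstick for adequate power.

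**1. The pilot figures.** With 69 people and six parameters (an intercept and a slope per arm), df=63 and the critical t is 1.998. SE = (upper - lower)/(2 × 1.998).

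- Interaction 1: SE = .172/3.996 = .043; t = .09/.043 = 2.09; p = .041. This agrees with the printed p<.05.
- Interaction 2: SE = .463/3.996 = .116; |t| = .23/.116, about 1.99; p = .051. This agrees with the printed p=.05, and the CI includes zero.

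**2. Converting within-arm r to interaction size.** In each arm let y = r·x + √(1-r²)·e. Then f² for the interaction is the mean squared deviation of the three slopes from their average, divided by the mean residual variance.

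- .3/0/0: mean slope .1; (.04+.01+.01)/3 = .020; residual (.91+1+1)/3 = .97; f² = .021.
- .5/0/0: mean slope .167; (.111+.028+.028)/3 = .056; residual (.75+1+1)/3 = .917; f² = .061.
- .3/-.3/-.3: mean slope -.1; (.16+.04+.04)/3 = .080; residual .91; f² = .088.
- .5/-.3/-.3: mean slope -.033; (.284+.071+.071)/3 = .142; residual (.75+.91+.91)/3 = .857; f² = .166.

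**3. Smallest detectable interaction.** By noncentral F with 2 and N-6 df and noncentrality N·f², 80% power needs f² of about .111 at N=90 and .140 at N=72. The first three patterns fall below both values; the fourth, and f²=.15, lie above both.

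**4. Power of the two-sided 2-df test of equal slopes.** The r patterns are simulated (200,000 trials each, pooled error on N-6 df). The last row is noncentral F.

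| Pattern (focal arm / other / other) | N=90 | N=72 |
|---|---|---|
| r = .3 / 0 / 0 | 20% | 16% |
| r = .5 / 0 / 0 | 50% | 40% |
| r = .3 / -.3 / -.3 | 66% | 55% |
| r = .5 / -.3 / -.3 | 91% | 83% |
| interaction f² = .15 | 91% | 83% |

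With no moderation in any arm the simulated rejection rate at N=90 is 5.0%, as it should be.

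**5. Sensitivity to the variance assumption.** With a common residual SD instead of equal outcome variance, the r=.3 patterns move by about one point or less. The .5/0/0 pattern rises to 58% (48% at N=72), still below 80%.

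**The case against.** *The claim may be right.* On an interaction f² of .15, N=90 has about 91% power, and 83% even with 72. This stands: a reader might infer that the trial is simply too small, and the documents do not support that. But the Protocol never states f². The metric in its context is within-condition r, which it reports for the pilot and uses again in the support rule. On that metric the answer depends on the pattern across arms.

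*The test is named.* OGRS is an omnibus method, so the natural reading is a 2-df interaction followed by probing. This largely stands, and it would be too strong to call the test undefined. What D6s omits is a sentence saying that the omnibus test decides. Indicator coding, the pilot's pairwise contrasts and the one-arm-against-two hypotheses leave room for another choice.

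*Other tests have more power.* For r=.3 in one arm only at N=90, counting either of the two focal-arm contrasts at unadjusted two-sided .05 gives about 32%, and one-sided focal-arm tests about 36% to 44%. So 20% is not a ceiling for every possible test, but all of these remain well below 80%.

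*Power at the pilot estimates proves nothing.* Correct. It would be about 66% and 61% at N=90, but those figures only restate p-values near .05, and nothing here rests on them. Likewise, the rule that a CI exclude zero governs which effects this trial will size. It does not formally disqualify the second pilot result; it shows how weak that result is as support.

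*N=72 is pessimistic.* It is: the 20% loss covers the whole study, the Aim 1 endpoint is at post-treatment, the analysis is intent-to-treat, and enrolment may exceed 90.

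**Conclusion.** The concern holds in a limited form. The statements that N=69 gave sufficient power and that N=90 suffices for medium to large effects are not supported by the two pilot interactions cited. As a general statement, the second does not hold on the within-arm r metric. For a moderator effect in one arm only, the two-sided 2-df test at N=90 has about 20% power at r=.3 and 50% at r=.5, while strongly opposed slopes (.5/-.3/-.3) or f²=.15 reach about 91%.

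The pilot's weakness and its distance from Aim 1 follow from the Protocol alone. The power figures rest on the assumptions listed in the working, including the 80% yardstick, since the Protocol sets no target. The point concerns an unsupported statement and how a null result would be read. It does not show that N=90 is the wrong sample size.

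**What to change.** 1. In D6s, replace the clause beginning "This sample size provided sufficient power" (through the words that introduce the two findings) with: *In this sample we observed*. Note that the second pilot CI includes zero. Delete the general sufficiency statement for N=90.
2. State that the two-sided 2-df omnibus moderator-by-arm interaction at .05 decides Hypotheses 1a-1c, with focal-arm contrasts and Johnson-Neyman regions as follow-up. Put the same statement in the SAP, which is silent on moderation. If the choice is made after data have been seen, say so.
3. Restate the sensitivity for that test with every pattern, favourable and unfavourable: *Assuming within-arm r=.3 as medium and r=.5 as large, equal arms, a normal moderator and equal outcome variance, power at N=90 (N=72) is about 20% (16%) for r=.3 in one arm only, 50% (40%) for r=.5 in one arm only, 66% (55%) for .3/-.3/-.3, 91% (83%) for .5/-.3/-.3, and 91% (83%) for an interaction f² of .15.*
4. Add: *A non-significant Aim 1 interaction will be reported with its confidence interval and will not be read as evidence of no moderation.* D6s already plans to interpret by estimates and CIs, so this only extends that to null results.

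Cost: wording and one decision about the deciding test. The stated sensitivity becomes less favourable. No extra participants are needed and trial conduct does not change.
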